Archival tumor tissue 12	x ¹²																	
[¹⁸ F]FDG-PET/CT ¹³	x ¹³							x ¹³										
Adverse Events ¹⁴	X	X	X	Х	Х	X	X	X	X	X	X	X	X	X	X	X		
Concomitant Therapy	х	X	X	Х	Х	Х	Х	X	X	Х	X	X	X	X	х	X		
Tumor assessment by CT/MRI RECIST 1.1 ¹⁵	x ¹⁵			•		•			•			x ¹⁵						
Tumor marker ¹⁶	x ¹⁶											x ¹⁶						
Termination of study medication															X			
Patient vital status																		X

^(*) Each treatment Cycle has a duration of 14 days

^(**) Patients who discontinue trial treatment prematurely should undergo the End of Treatment (EOT) visit as soon as possible. If assessments due at EOT are not completed, they may be performed at the 30-Day Safety FUP Visit.

Page 15 of 165

Proprietary confidential information © 2023 Boehringer Ingelheim International GmbH or one or more of its affiliated companies

(***) The 30-Day Safety Follow-up visit is the End of Residual Effect Period visit (EOR) which must happen at the earliest 30 (+ 5) days after the last dose of treatment (see Section 6.2.3.2). †Additional follow-up visits for progression after the 30-Day safety follow-up visit will be performed for patients who discontinue for reasons other than progression or death. Follow-up continues until progression per the imaging schedule (see Section 5.1). The follow-up visits for survival status will be performed every 12 weeks (+/-7 days)(in person or by telephone) until death, lost to follow-up, withdrawal of consent, or end of the whole trial (see Section 6.2.3.3).

For every cycle, the interval between two dose administrations must be always at least 14 days.

¹Written informed consent must be obtained before any protocol specific screening assessments are performed. Re-consenting may become necessary when new relevant information becomes available and should be conducted according to the Sponsor's instructions. Separate consent is to be obtained for optional biomarker sampling.

²Eligibility for further treatment should be confirmed prior to dosing on Day 1 of each cycle from Cycle 2 onwards by confirming the patient has not met any criteria for protocol discontinuation as described in section 3.3.4.1 and absence of any adverse event requiring treatment discontinuation (section 4.1.2.3).

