¹²Pre-treatment fresh tumor biopsy collections for biomarker analyses are considered mandatory in phase Ib. Only non-significant risk procedures per the investigator's judgment will be used to obtain any biopsies specified in this study. For each biopsy, a minimum of 2 core needle biopsies needs to be freshly taken between screening and before first study treatment (Cycle 1 Day 1) after eligibility has been confirmed. In case a fresh pre-treatment tumor biopsy cannot be obtained due to before mentioned reasons an archived tumor tissue specimen obtained within ≤6 months of screening must be submitted. In case the patient undergoes baseline tumor biopsy, an archival tumor tissue must also be submitted (mandatory) regardless of the date of collection. An additional fresh tumor biopsy should be taken on Cycle 2 Day 3 (optional) and/or at disease progression (optional) for a patient in which a fresh biopsy has been successfully obtained before first study treatment (refer to Section 5.4.1). ¹³[¹⁸F]FDG-PET/CT should be performed at baseline within 14 days (±7 days) prior to treatment start (Cycle 1 Day 1). A second [¹⁸F]FDG-PET/CT will be performed at the 8 week tumor assessment timepoint. It may be performed together with standard CT assessment if feasible.

¹⁴After the individual patient's end of the trial, the investigator should report only any occurrence of cancer, related SAEs and related AESIs of which the investigator may become aware of and only via the SAE form, see Section 5.2.6.2.1.

¹⁵Tumor assessment should include CT scans or MRI of the chest, abdomen, pelvis, and if clinically indicated imaging of any other known or suspected sites of disease (e.g. brain, bone). The same radiographic procedure must be used throughout the study. At least one prior pre-study digital scan of the target lesion should be sent to the central imaging facility of an independent vendor if available. Tumor assessment does not need to be performed at the Screening visit if there are valid results available from assessments which were performed as part of routine clinical practice within 28 days prior to start of treatment. Repeat tumor assessment will be performed every 8 weeks (± 7 days) until progression or start of further treatment for disease:

Repeat imaging at > 4 weeks to confirm response. In the event of early discontinuation for reasons other than progressive disease or interruption/delay of treatment the tumor assessment

schedule should not be changed.

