7.3.1 Primary endpoint analyses

Phase Ia: In order to determine the MTD, the number of patients with DLTs will be assessed per dose level in phase Ia. The MTD will be determined as described in Section 7.1. Patients with DLTs that occurred during the first two treatment cycles and later cycles may be tabulated separately.

For doses that will be recommended for phase Ib, totality of data will be considered including efficacy and PK. Details are described in Section 3.1.1.

Time frame: Database lock (DBL) will occur when either MTD is found or the recommended dose range for phase Ib is determined, and all the patients have had at least 2 post-baseline tumor assessment timepoints excluding patients who have discontinued earlier.

Phase Ib:

The primary endpoints in the dose-expansion part are objective response (OR) and PFS derived from the data of all cycles. The PFS will be summarized using PFS4 rate, defined as the proportion of patients with PFS >= 4 months, and will be presented descriptively. Objective response will be analyzed in terms of objective response rate (ORR), defined as the proportion of patients with best overall response of complete response (CR) or partial response (PR). For each dose level, the proportion of patients with objective response (CR and PR) will be calculated with 95% confidence interval.

The observed response rate and PFS4 rate for different dose levels will be compared to recommend the optimal dose level (RP2D). If applicable, a Bayesian hierarchical model will be used to get the adjusted response rate for each dose level, and comparisons will be made among different dose levels to make a recommendation on the optimal dose level (RP2D).

Time frame: The database lock will occur after all treated patients have had at least three post-baseline tumor assessment timepoints (unless patients discontinue the treatment early due to any reasons). A clinical trial report will follow.

Page 100 of 165

Proprietary confidential information © 2023 Boehringer Ingelheim International GmbH or one or more of its affiliated companies

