5. ENDPOINTS(S)

5.1 PRIMARY ENDPOINT(S)

The primary endpoints in Phase Ia are:

- Maximum tolerated dose (MTD) defined as the highest dose with less than 25% risk of the true DLT rate being equal or above 33% during the MTD evaluation period as determined by the BLRM defined in section 7 of the CTP. For the definition of DLTs, refer to Section 5.2.6.1.5 of the CTP.
- Number of patients with DLTs in the MTD evaluation period.

The primary endpoints in Phase Ib are:

- Objective response based on RECIST 1.1 criteria. Objective response is defined as best overall response of complete response or partial response, where best overall response is the best response recorded from the start of the study treatment until the earliest of disease progression, death or last evaluable tumor assessment and before start of subsequent anticancer therapy.
- Progression-free survival (PFS) is defined as the time from first treatment administration until tumor progression according to RECIST 1.1 or death from any cause, whichever occurs earlier.

A detailed definition of objective response and PFS is given in section 9.1.

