6.7 BASELINE, TIME WINDOWS AND CALCULATED VISITS

Study days and visits will be labelled according to the CTP's flow chart.

Unless otherwise specified, baseline is defined as the time point closest to and prior to the first administration of study treatment. Note that for some study procedures (e.g. body weight, vital signs, laboratory tests), baseline may be the measurement made on the same day the study treatment was started. In such cases, these measurements will be assumed to have been taken according to the protocol, i.e. prior the first administration of BI 905711.

For laboratory parameters for which not only the examination date but also the sampling time was recorded, examination time should be taken into consideration when defining baseline. That is a laboratory measurement on the same date as the first administration of BI 905711 is considered as baseline if and only if the examination time of the laboratory measurement is before the first administration of BI 905711.

7. PLANNED ANALYSIS.

The following standards for End-Of-Text tables are defined:

- The set of summary statistics for continuous data is: N / Mean / Standard Deviation (StD) / Min / Median / Max. For tables that are provided for endpoints with some extreme data, median, quartiles, and percentiles should be preferred to mean, standard deviation, minimum, and maximum. If not otherwise specified, the abbreviation Pxx should be used for displaying the xxth percentile. Other than the Min and Max, all statistics will be presented to one more decimal place than the raw data.
- Tabulations of frequencies for categorical data will include all possible categories and will display the number of observations in a category as well as the percentage (%) relative to the respective treatment group (unless otherwise specified, all patients in the respective patient set whether they have non-missing values or not). The precision for percentages will be one decimal place. The category "missing" will be displayed only if there are actually missing values.
- For time-to-event analysis tables the set of statistics is: number of patients [N(%)], number of patients with event [N(%)], <time to event> [months] followed by 25th percentile (P25), median, 75th percentile (P75) and number of patients censored [N(%)]. If not specified otherwise the duration as well as the time to event will be displayed in months.

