Where applicable, conversion from days to weeks, months, and years will be as follows:

- Weeks = days \div 7
- Months = $(days \times 12) \div 365.25$
- Years = days \div 365.25.

General aspects for PK

Descriptive data analysis of PK endpoints and concentrations will be performed according to BI procedures.

Plasma concentration data and parameters of a subject will be included in the statistical pharmacokinetic (PK) analyses if they are not flagged for exclusion due to a protocol deviation relevant to the evaluation of PK (to be decided no later than in the Report Planning Meeting) or due to PK non-evaluability (as revealed during data analysis, based on the criteria specified below). Exclusion of a subject's data will be documented in the CTR.

Important protocol deviations may be

- Incorrect trial medication taken, i.e. the subject received at least one dose of trial medication the subject was not assigned to
- Incorrect dose of trial medication taken
- Use of restricted medications

Plasma concentrations and/or parameters of a subject will be considered as non-evaluable, if for example.

• Missing samples/concentration data at important phases of PK disposition curve.

Plasma concentration data and parameters of a subject which are flagged for exclusion will be reported with its individual values but will not be included in the statistical analyses. Only concentration values within the validated concentration range and actual sampling times will be used for the calculation of pharmacokinetic parameters. Concentrations used in the pharmacokinetic calculations will be in the same format as in the bioanalytical report (that is to the same number of decimal places provided in the bioanalytical report).

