7.4.1 Main Analysis

The primary analyses for Phase Ia:

In order to identify the MTD of the trial, the number of patients at each dose level that had DLT during the MTD evaluation period will be presented, excluding patients who discontinue during the first treatment cycle for reasons other than a DLT. The BLRM as described in Section 7.1 of the CTP will be analyzed using the number of patients at each dose that had DLTs during the MTD evaluation period among the patients in the MTD set. The prior defined in Table 7.1: 1 of the CTP will be used for the analysis. The resulting posterior distribution of the DLT rates of the doses tested during the trial will be summarized using their mean, SD, 2.5% quantile, median, and 97.5% quantile. Additionally, the posterior probabilities of the DLT rate lying in the intervals [0, 0.16) (under dosing), [0.16, 0.33) (target dosing), and [0.33, 1] (overdosing) will be computed and listed for each dose. The posterior probabilities of under dosing, target dosing, and overdosing of the tested dose levels will additionally be visualized in a bar diagram that further displays which of the dose levels satisfy the EWOC criterion.

In addition, the number of patients with DLTs that occurred during the entire treatment period will be summarized at each dose level.

The primary analyses for Phase Ib:

The primary endpoints in the dose-expansion part are objective response (OR) and PFS derived from the data of all cycles. The PFS will be summarized using PFS4 rate, defined as the proportion of patients with PFS >= 4 months, and will be presented descriptively together with 95% confidence intervals. Objective response will be analyzed in terms of objective response rate (ORR), defined as the proportion of patients with best overall response of complete response (CR) or partial response (PR). For each dose level, the proportion of patients with objective response (CR and PR) will be calculated with 95% confidence interval.

Kaplan-Meier estimates will be used to display the distribution of PFS for each treatment group on a Kaplan-Meier curve. To support the plot, estimated survival probabilities at specific time points of interest (scheduled imaging time points) will be tabulated along with 95% CIs using Greenwood's variance estimate. In addition, the Kaplan-Meier estimates will be used to provide estimates of the median, 25th, and 75th percentiles.

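### PFS4 is planned as a plain proportion of an endpoint that can be censored, and no 4-month Kaplan-Meier estimate is tabulated; adding one at 121.75 days is a cheap improvement

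*SAP*

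**What the plan says.** PFS is one of two Phase Ib primary endpoints, defined as a time to event (protocol 2.1.2, SAP 5.1). SAP 7.4.1 summarises it as follows: "The PFS will be summarized using PFS4 rate, defined as the proportion of patients with PFS >= 4 months", with a 95% CI. Protocol 7.3.1 uses the same measure, "defined as the proportion of patients with PFS >= 4 months, and will be presented descriptively". Neither names Kaplan-Meier as the estimator of PFS4.

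SAP 7.4.1 also plans a Kaplan-Meier curve per treatment group, quartiles, and a table with Greenwood intervals in which "estimated survival probabilities at specific time points of interest (scheduled imaging time points) will be tabulated".

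The rules in SAP 7 that bear on this are:

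- For categorical data, percentages are by default taken over every patient in the analysis set, whether or not the value is missing.
- Time-to-event tables end with the "75th percentile (P75) and number of patients censored [N" and percentage, so censoring is expected.
- A "conversion from days to weeks, months, and years will be as follows" rule sets months as days × 12 / 365.25.

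Protocol 7.5 rules out imputing missing efficacy data, and SAP 6.6 leaves missing data missing unless specified otherwise.

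SAP 5.1 adds: "A detailed definition of objective response and PFS is given in" section 9.1. That section has no readable content in the public copy, so its content is unknown; it cannot be called absent.

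**The concern.** A plain proportion treats PFS4 as a yes/no outcome known for everyone. A patient whose follow-up ends without progression before 4 months has no known answer. On the visible defaults that patient stays in the denominator and adds nothing to the numerator, as if progression or death had occurred. The Kaplan-Meier method that would use the partial follow-up is already planned, but its table has no row at 4 months.

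The stake is the accuracy of one reported estimate. The development programme has been terminated (protocol 1.3) and no hypothesis test is planned (protocol 7.2). The abbreviated report still contains the primary endpoint analyses (SAP 4), so the PFS4 figure will be published and read.

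**Working it through.** **Plan's own figures.** Phase Ia reported progression-free status at 4 months or more in 3 of 26 CRC patients: 3/26 = 11.5% (protocol 1.2), a plain proportion of all patients. Table 7.7: 1 of the protocol plans with PFS4 of 60% (positive scenario) and 35% (negative scenario). The planned CRC cohort size is 15 (protocol 7.7).

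**Where 4 months falls.** 4 × 365.25 / 12 = 121.75 days. Scans were due every 8 weeks ± 7 days: days 56, 112 and 168. Day 112 is 112 × 12 / 365.25 = 3.68 months and day 168 is 5.52 months. The week-16 window closes on day 119, so progressions found on days 113 to 119 fall after the day-112 row but before 4 months. That row is therefore not a substitute.

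**Can a patient be censored before day 121.75?** Protection is fairly good. Before protocol v7.0, for patients who stopped for reasons other than progression or death, "Follow-up continues until progression per the imaging schedule". Database lock waits for three post-baseline assessments, about day 168. Three routes remain:

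1. The lock rule exempts patients who stop treatment early (protocol 7.3.1).
2. Scans run only "until progression or start of further treatment for disease".
3. Under v7.0 (Cycle 6 onward) required follow-up ends at EOR, 30 to 35 days after the last dose (protocol 6.2.3.2 and 6.2.3.3). With 14-day cycles and nominal days:

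| Last dose | Day | EOR days | Before 121.75? |
|---|---|---|---|
| Cycle 6 Day 1 | 71 | 101–106 | yes |
| Cycle 7 Day 1 | 85 | 115–120 | yes |
| Cycle 8 Day 1 | 99 | 129–134 | no |

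**Bias of the plain proportion.** Let S(4) be the true 4-month PFS and c the fraction of patients with a censoring time before month 4, independent of prognosis. A patient counts as an achiever only if event-free and uncensored at 121.75 days, so the expected proportion is S(4) × (1 − c) and the bias is −c × S(4). With c = 1/15:

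| S(4) | Source | c × S(4) | Bias, points |
|---|---|---|---|
| 60% | positive scenario | 0.600/15 = 0.040 | −4.0 |
| 35% | negative scenario | 0.350/15 = 0.023 | −2.3 |
| 11.5% | Phase Ia CRC | 0.115/15 = 0.008 | −0.8 |

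At c = 0 the bias is zero. In a simulation with n = 15 and independent censoring, Kaplan-Meier at 121.75 days gave 0.600–0.601, 0.350–0.352 and 0.115–0.117 for these three rates over assumed c of 10–30%.

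**Worked example (assumed data, n = 15).** Nine reach 4 months, five have events, one is censored early. The plain proportion is 9/15 = 60.0%. Kaplan-Meier depends on when the censoring falls:

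- before any event: 9/14 = 64.3%;
- after two events: 13/15 × 9/12 = 65.0%;
- after all five: 10/15 = 66.7%.

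**Sampling error.** For the middle case the Greenwood SE is 0.127, so the 95% half-width is 1.96 × 0.127 = 0.249, about ±25 points. At 11.5% a binomial approximation gives 1.96 × √(0.115 × 0.885 / 15) = 0.161, about ±16 points. The bias is well inside both.

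**If censoring is informative.** Suppose 20% of patients leave shortly before they would have progressed (assumed). In simulation Kaplan-Meier then gives 66% for a true 60% and 43% for a true 35%, while the plain proportion gives 59% and 34%.

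**The case against.** The plain count over all treated patients is a recognised, conservative convention: those shown to be progression-free at 4 months, out of everyone. It matches the Phase Ia figures. When censoring hides imminent progression it is closer to the truth than Kaplan-Meier, and stopping early or starting other therapy in refractory cancer is where that is plausible. SAP 9.1 may already hold a PFS4 rule. The planned curve can be read at 4 months by eye, and the overall number censored is already requested. The v7.0 route is narrow: it needs a stop without progression, and nominal days are the earliest possible. For a last dose at Cycle 7, cumulative delays of 2 to 7 days move EOR past 121.75.

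Most of this stands, and it is why the plain proportion should be kept. It does not supply a tabulated 4-month estimate with an interval, or the number censored before 4 months. Without these a reader cannot tell whether the conservative count matters.

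A reader might infer more than the documents support:

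- *That the counting rule is open, so early-censored patients might equally be dropped or counted as achievers.* The visible default keeps all patients in the denominator, which excludes dropping. Counting them as achievers would need a rule that is not visible.
- *That PFS4 could be wrong by as much as 18 points.* That is 0.30 × 60%, and it needs an assumed 30% early censoring. The documents give no such rate, and the follow-up and lock rules point to limited early censoring.
- *That Kaplan-Meier would deal with any early censoring.* It does so only if censoring is non-informative.

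**Conclusion.** The point holds as a cheap improvement. On the visible text PFS4 is a plain proportion of an endpoint that can be censored, and the default rules turn an early-censored patient into a non-achiever. With non-informative censoring the bias is downward by c × S(4): about 4.0, 2.3 or 0.8 points for one such patient in a cohort of 15 at 60%, 35% or 11.5%, and nothing if nobody is censored early.

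This rests on three things: SAP 9.1 not setting a different rule, independence of censoring and prognosis, and an assumed c. Recruitment stopped during Phase Ib (protocol 3.1.2), so actual cohorts may be smaller than 15. One patient would then weigh more, but sampling error would grow too.

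The missing 4-month row in the planned table is visible in 7.4.1 whatever SAP 9.1 contains. A reader might also infer that the dose recommendation is compromised. With the programme terminated and all analyses descriptive, the documents do not support that.

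**What to change.** In SAP 7.4.1, report PFS4 per cohort as the Kaplan-Meier estimate at 121.75 days with a Greenwood-based 95% CI on the log-log scale, and add that row to the planned table. Keep the plain all-patients proportion beside it as the conservative figure, with the number of patients censored before 4 months in each cohort. Record the difference from protocol 7.3.1 in SAP 4. If SAP 9.1 already specifies this, a cross-reference in 7.4.1 is enough.

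The cost is a sentence, a table row, a count and an entry in SAP 4, using methods already planned. There are three limits:

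- At about 15 patients the Greenwood interval is approximate. With 12 events, 1 censored and 2 achievers, the plain-scale lower limit can fall to about −4%; the log-log scale avoids this.
- Kaplan-Meier overstates PFS if early censoring is informative, which is why both figures should be shown.
- If the Bayesian hierarchical model of protocol 7.7 is still run as a binomial model, a Kaplan-Meier estimate does not enter it directly, so its rule for early-censored patients should be stated.

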7.5 SECONDARY OBJECTIVE ANALYSIS

7.5.1.1 Main analysis

There is no key secondary analysis as no key secondary endpoint has been specified in the protocol.

7.5.2 (Other) secondary objective analysis

Descriptive analysis of the following pharmacokinetic parameters will be performed for BI 905711 in phase Ia and phase Ib as outlined in section 7.3.5 in CTP and according to BI standards if applicable and feasible

- C_{max}: maximum measured concentration of BI 905711 in plasma
- AUC_{0-t2}: area under the concentration-time curve of BI 905711 in plasma

Phase Ia:

The Objective response will be analyzed the same way as the primary endpoint in Phase Ib.

Phase Ib:

The Number of patients with treatment emergent AEs, duration of overall response and disease control will be analyzed by descriptive statistics. Disease control rate will be analyzed the same way as ORR. Tumor shrinkage will be analyzed by descriptive statistics and by treatment. Waterfall and spider plots will be provided.

As of March 2023 the study was terminated due to lack of efficacy signal and it was decided to produce an abbreviated report for CTR. The abbreviated CTR would include primary and secondary endpoint analyses. There would be limited analyses provided from statistics and programming for PK and this would only include listing of consistency checking PK data. The PK group (TMCP) would provide analyses for Cmax and AUC.

Additional PK analysis

The analysis of standard PK parameters is performed according to BI internal standards (2).

Attainment of steady state

The attainment of steady state will be inspected graphically. The attainment of steady state will be explored using the trough plasma concentrations before the Nth administration of BI 905711 in each cycle. Pair-wise comparisons of the differences between time points will be explored by using a repeated measures linear model on the logarithmic scale of trough plasma concentration including 'subject' as a fixed effect, and 'time' as a repeated effect in the model. This analysis will be done for the dose groups at 0.2 mg/kg, 0.6 mg/kg, 1.2 mg/kg, 2.4 mg/kg, 3.6 mg/kg and 4.8 mg/kg where each dose group is analysed separately. The structure of the within-subject covariance matrix generally is not known in advance and will be chosen to be "unstructured", in case of convergence problems Huynh-Feldt, Toeplitz or Autoregressive (AR1) will be chosen (based on Akaike's information criterion). On the logarithmic scale, the linear model equation for the investigation of steady state is:

$$Y_{ij} = \mu + \tau_i + \epsilon_{ij}$$

where

 Y_{ij} logarithm of the trough plasma concentrations of BI 905711 for subject j at time i, where i = 1, 2, 3, 4 indexing time point and j=1, 2, ..., n indexing subject

μ the overall mean

 τ_i the effect associated with time i (discrete repeated effect)

 ε_{ij} random error associated with subject j at time i (assumed to be independent and identically normally distributed).

This analysis will be accomplished by fitting the repeated measures model (MIXED procedure). For the approximation of the degrees of freedom the Kenward and Roger method will be used. The Akaike information criterion (AIC) will be used to select the best fitting covariance structure.

Subsequently, adjusted least square means and two sided 95% confidence intervals will be calculated and back transformed by exponentiation. Furthermore pairwise comparisons of the log-transformed differences between all subsequent time points (log(trough concentration at time i/trough concentration at time k) = log(trough concentration at time i) - log(trough concentration at time k) where k>i) will be performed including the calculation of two sided 95% confidence intervals using residual error from ANOVA.

Dose proportionality analysis

Dose proportionality will be explored using the power model that describes the functional relationship between the dose and pharmacokinetic endpoints as follows.

$$\exp(Y_{ij}) = \alpha' * \exp(X_i)^{\beta} * \epsilon'_{ij}$$

Putting $\alpha' = exp(\alpha)$ and $\epsilon'_{ij} = exp(\epsilon_{ij})$, after taking natural logarithms this model is converted to a linear form as follows.

$$Y_{ij} = \alpha + \beta * X_i + \epsilon_{ij}$$

 Y_{ij} = logarithm of the pharmacokinetic endpoint (i.e. C_{max} , AUC_{0-tz} , $AUC_{0-\infty}$ for Cycle 1 and, if applicable, C_{max} and AUC_{0-tz} for Cycle 2) for subject j at dose level i, where i = 1, 2, ... indexing dose level and j = 1, 2, ... indexing subject

 α = intercept parameter

 β = slope parameter

 $X_i = logarithm of dose level i$

 ε_{ij} = residual error associated with subject j at dose level i (assumed to be independent and identically normally distributed).

This equation can be fit as a linear regression model. A 95% confidence interval for the slope will be computed. In the ideal sense, dose proportionality would correspond to a value of 1 for the slope parameter β in the power model. Dose proportionality would be assumed when the 95% CI for β includes 1.

As of March 2023 the study was terminated due to lack of efficacy signal and it was decided to produce an abbreviated report for CTR. The abbreviated CTR would not include any analysis in this section of steady state or dose proportionality etc.

